6	6.1 6.2 6.3 6.4 6.5 6.6 6.7	REGULATORY AND ETHICAL ISSUES 36 PROTOCOL DEVELOPMENT 36 PROTOCOL MANAGMENT 37 INFORMED CONSENT REQUIREMENTS 38 IRB DOCUMENTATION 38 QUALITY CONTROL AND QUALITY ASSURANCE 39 DATA HANDLING 39	3
	'.1	COSTS	ĺ
-	. 1	ALIFICATIONS AND SOURCE OF SUPPORT	ĺ
9. 10.		ERENCES	r

PROTOCOL SYNOPSIS

Protocol Title:	Autoantibody Reduction Therapy in Patients with Idiopathi Pulmonary Fibrosis				
Protocol Number:	PRO13110227				
NCT Number:	NCT0196409				
Version # and Date:	Version 3.1 / December 11,	2014			
Clinical Phase:	Phase II clinical investigation	n			
Trial Site:	Multi-Center Trial				
Principal Investigator:	[name]				
	Professor of Medicine Division of Pulmonary, Allergy, and Critical Care Medicine University of Alabama at Birmingham [name]				
Co- Principal Investigator:	[name] Co- Principal Investigator University of Pittsburgh				
Co-Investigators:	[name] Co-Investigator Temple University [name] Co-Investigator University of Chicago [name], MD Co-Investigator University of Alabama at Birmingham	[name] Co-Investigator Geisinger Medical Center [name] PhD Co-Investigator University of Pittsburgh [name] Co-Investigator University of Alabama at Birmingham			
Participating Medical Centers:	 University of Pittsburgh Medical Center Geisinger Medical Center Temple University Medical Center University of Chicago Medical Center University of Alabama at Birmingham 				
Data Coordinating Center:	Epidemiology Data Center University of Pittsburgh Graduate School of Public Health				

Sponsor:	National Heart, Lung, and Blood Institute (HL119960)				
Study Rationale:	On the basis of substantial preliminary data, we hypothesize that autoantibodies play a pathogenic role in the progression of idiopathic pulmonary fibrosis (IPF). Autoantibody-mediated lung diseases are often refractory to treatments with nonspecific agents, including glucocorticoids. Rituximab, the experimental therapy here, is mechanistically targeted to decrease autoantibody concentrations. We hope that autoantibody-targeted treatments could result in significant benefit for a lung disease that has, until now, been almost invariably inexorable. This clinical trial has the potential to profoundly affect current paradigms and treatment approaches to patients with IPF.				
Study Objectives:	The primary goal of this multicenter, randomized, double-blind, Phase II clinical trial is to determine effects of rituximab on selected relevant immunological parameters of IPF patients, in comparison to effects of placebo alone. We anticipate the findings of this will lead to larger incremental trial(s) to definitively establish the clinical efficacy of this treatment.				
Study Hypothesis:	Our central hypothesis is that antibody-mediated autoimmunity can play an important role in IPF. We propose to begin to test our central hypothesis by establishing the efficacy and duration of autoantibody reductions by rituximab in IPF patients.				
Study Aims:	 To conduct a proof-of-concept, mechanistically-driven trial to reduce autoantibodies against HEp-2 cells. To determine the effects of the experimental treatment (rituximab), compared to placebo therapy, on secondary endpoints of: 1.) anti-heat shock protein 70 (HSP70) concentrations; 2.) changes in forced vital capacities; 3.) acute IPF exacerbation incidences; 4.) survival; 5.) hospitalization rates; and 6.) adverse event-rates. 				
Study Design:	 Following screening assessments, IPF patients who meet all inclusion/exclusion criteria will be randomly assigned to receive one of the following treatments in a ratio of 1:1: Arm A (n=29) - Rituximab Treatment: Premedications, consisting of 100 mg methylprednisolone I.V., and P.O. acetaminophen and diphenhydramine, will be followed by rituximab 1 g. I.V. Arm B (n=29) - Placebo Treatment: 				

	receive the premedication regimen (above), and placebo infusions of dextrose 5% in water (D5W), in lieu of rituximab, that are indistinguishable from the rituximab unit doses. Both treatments (premedications + either rituximab or D5W will be repeated 14 days after the first treatments. Patients will be monitored carefully for occurrence of adverse events, and changes in vital signs. Patients will be followed for a total of 9 months after their first study treatments.				
Planned Sample Size:	A total of 58 subjects will be enrolled in this multi-center trial from 5 participating medical centers				
Duration of Study:	Nine months				
Inclusion Criteria:	 Diagnosis of IPF, not established >5 years from the enrollment date, that fulfills ATS/ERS Consensus Criteria (1). Ability and willingness to give informed consent. Age 50-85 years old. Ambulatory. Presence of autoantibodies against HEp-2 cells at plasma titrations of ≥1:20, the assay for the primary endpoint. 				
Major Exclusion Criteria:	 Diagnosis of current infection, proven or suspected by participating physicians based upon their clinical assessments. Presence of active hepatitis B or C, or HIV infection. History of conventional autoimmune syndromes (e.g., systemic lupus erythematosus, scleroderma, rheumatoid arthritis, myositis, Sjogren's syndrome, anti-neutrophil cytoplasmic autoantibody vasculitis, Goodpasture's syndrome) by clinical evaluation or positive conventional autoimmune serologic tests (i.e., ANA, RF, Anti-Ro, ANCA, Anti-LA, Anti-RNP, Anti-Jo-1). History of reaction to murine-derived products or any of the trial medications, or prior exposures to human-murine chimeric antibodies. 				

- 5) Malignancy, excluding basal or squamous cell skin cancer or low-risk prostate cancer. The latter is defined as stage T1 or T2a with PSA less than 10 ng/dl. Rituximab is not known to promote cancer progression, and these criteria are within current guidelines.
- 6) Unwillingness to complete post-treatment surveillance for 9 months.
- Diagnosis of major morbidities (aside from IPF) expected to interfere with subjects' study participation for 9 months.
- 8) Treatment for >5 days within the preceding month with >10 mg. prednisone (or equivalent corticosteroid) or any treatment during the preceding month with a potent cellular immunosuppressant (e.g., cyclophosphamide, methotrexate, mycophenolate, azathioprine, calcineurin inhibitors, etc.).
- 9) Uncontrolled diabetes or hypertension that precludes safe treatment with methylprednisolone.
- 10) Concurrent participation in other experimental trials.
- 11) Pregnancy or unwillingness to use contraception during the duration of the study among female participants with child-bearing potential. The safety of rituximab during pregnancy has not been established.
- 12) Ratio of forced expiratory volume in 1 second to forced vital capacity (FEV₁/FVC) <70% of predicted values.

Study Endpoints:

· Primary endpoints:

The primary endpoint is reduction of autoantibody titers to HEp-2 epithelial cells, comparing baseline measures of each individual to results of their interval measures during the next 9 months.

Secondary endpoints:

Secondary endpoints are: 1.) treatment-related effects on anti-HSP70 autoantibody concentrations, 2.) forced vital capacities, 3.) incidences of acute IPF exacerbations, 4.) survival durations; 5.) hospitalization rates; and 6.) adverse event-rates

1. OBJECTIVE, SPECIFIC AIMS, BACKGROUND, AND SIGNIFICANCE

1.1 OBJECTIVE

The primary goal of this randomized, multi-center, double-blind Phase II clinical trial is to determine the effects of rituximab treatment in terms of autoantibody reductions (magnitude and duration) in IPF patients. We anticipate the findings here will lead to larger incremental trial(s) to determine actual clinical efficacy of this treatment.

1.2 SPECIFIC AIMS

Hypothesis: Our central hypothesis is that antibody-mediated autoimmunity plays an important role in IPF progression. A corollary of this hypothesis is that treatments that reduce autoantibodies in these patients will have a favorable effect on the natural history of this disease. The studies proposed here are primarily designed to determine the magnitude and duration of autoantibody reductions affected by rituximab, as a prelude to design of a definitive Phase III efficacy study. Nonetheless, we hope that experimental treatments may result in clinically-relevant beneficial effects as determined by secondary endpoints: preservation of forced vital capacities or reductions of acute exacerbation incidences.

Specific Aims:

1. To conduct a proof-of-concept, mechanistically-driven trial to reduce autoantibodies against epithelial HEp-2 cells among IPF patients.

We hypothesize the experimental treatment with rituximab will more effectively reduce anti-HEp-2 autoantibodies, the primary endpoint of this clinical trial, compared to placebo treatment.

To determine the effects of the experimental rituximab treatment on secondary endpoints of anti-HSP70 autoantibodies, preservation of forced vital capacities, survival, need for hospitalizations, incidences of acute IPF exacerbations, and adverse event-rates.

We hypothesize the experimental treatment will also have a demonstrable effect on these secondary endpoints, in comparison to placebo therapy, and will have acceptable adverse event profile.

Findings of this study will also further develop the potential of focused immunologic assays as prognostic and disease phenotyping tools of individual IPF patients. We anticipate this proposal will establish the feasibility of autoantibody-targeted interventions, and results here will be a nidus for subsequent incremental clinical trials in this population.

The preliminary data that support our central hypothesis are novel findings from a series of innovative investigations.

1.3 BACKGROUND

Idiopathic pulmonary fibrosis (IPF) is a morbid interstitial lung disease that is characterized by lung parenchymal fibroproliferation (1-4). IPF manifests with progressive shortness of breath and hypoxemia. The absence of a valid pathological paradigm has precluded the rational selection of mechanistically-targeted therapy. Only two medications, whose mechanisms of action remain largely speculative (pirfenidone and nintedanib), have been recently shown to have partial efficacy for IPF. IPF continues to have a worse prognosis than many common malignancies, with a median survival of approximately 3 years from the time of diagnosis.

Our recent studies and others (5-21), support an autoimmune pathogenesis, leading us to posit the central hypothesis of this proposal: Antibody-mediated autoimmunity plays an important role in IPF progression. Among these findings, B-cell follicular-like aggregates are evident in IPF lungs (5,6,20), along with over-expressions of immunoglobulin (Ig) genes (8). Antigen-antibody (immune) complexes with considerable pathogenic potential are present in sera, bronchoalveolar lavage (BAL) and lung parenchyma of IPF subjects (7,9,14,20). Injurious complement deposits are also common in IPF lungs (20). Enhanced B-cell differentiation induced by antigen exposure and increased circulating levels of B-lymphocyte stimulating factor (BLyS) are characteristics of autoantibody-mediated diseases, and are similarly increased and proportionate to disease activity among IPF patients (20). Various circulating antibodies with self-avidities are detectible in ~80% of IPF cohorts (10,14). Several of these IPF autoantibodies exert direct cytopathic or other function-altering effects, and/or are associated with clinical manifestations and prognoses of the afflicted individuals (9-17). We have also recently found that CXCL13, an important mediator for B-cell trafficking to inflammatory foci, is similarly increased in lungs and plasma of IPF patients, proportionate to their disease activity, and inversely proportionate to their survival (21).

Other autoantibody-mediated lung diseases are refractory to nonspecific therapies, notably including steroids. In contrast, however, specific treatments to remove or reduce autoantibodies are now a mainstay of therapy for anti-donor HLA antibody-mediated lung transplant rejection and other patients with autoantibody-mediated lung diseases (22-28).

Pilot Study of Autoantibody-Targeted Therapy in IPF. Based on these and other interrelated findings, we initiated an experimental trial to reduce autoantibodies in critically-ill patients with rapidly progressive IPF (28). The first seven (7) subjects were treated at Presbyterian University Hospital of the University of Pittsburgh Medical Center (PUH-UPMC). The most recent subject (#8) was treated by [name] at the University of Texas Medical Branch (UTMB) in Galveston, Texas.

All subjects fulfilled ATS/ERS diagnostic criteria (1) and were having very severe acute IPF exacerbations (4). None had other causes of lung dysfunction per extensive clinical evaluations, nor abnormal conventional autoantibody tests (14). None of the subjects were transplantation candidates at their presentations due to contraindications of advanced age, irreparable coronary artery disease or not having already undergone the necessary transplantation evaluations. This was a pilot, "compassionate-use" trial to explore feasibility and gain insights for incremental studies.

Rituximab onset of clinical benefit can take weeks (29-39). Since these subjects were expected to die within days, we used plasma exchange (PEX) to rapidly remove autoantibodies and "buy time" for rituximab effects. PEX consisted of 1.5x plasma volume exchanges with 95-100% replacement using albumin:saline (3:1), on days 1-3, and 5-6. The number of PEX treatments (five) was chosen empirically *a priori*, as a balance of risk and expense in this novel application *vs.* the potential to see

some benefit. PEX has rapid onset, but effects have limited duration in the absence of other treatments (40,41). Rituximab (1 g I.V.) was given after the last PEX and 1 week later, without apparent complications.

1.4 SIGNIFICANCE

If our hypothesis is correct, treatments that reduce autoantibody production (e.g., rituximab) will have beneficial effects in IPF patients. The proposed clinical trial here will generate important preliminary data regarding the magnitude and duration of rituximab effects on autoantibody production in IPF patients. These data will be essential for design of a subsequent clinical efficacy (Phase III) study.

2 RESEARCH DESIGN AND METHODS

2.1 CLASSIFICATION AND METHODOLOGICAL DESIGN

This is a multi-center, randomized, double-blind, placebo-controlled Phase II clinical trial to determine the effects of rituximab on autoantibody production in IPF patients.

2.2 STUDY DESIGN

Participants will be recruited from the ambulatory IPF patient populations among the collaborating institutions.

Following completion of screening and eligibility assessments, N=58 subjects will be randomly assigned to one of two cohorts intended to receive either rituximab or placebo, in a ratio of 1:1. The rituximab (or placebo) will be administered over two doses (1 g each), following premedications, with a 14 day interval in between these replicate treatments.

All patients will have physiological assessments that are standard of care for IPF patients, including initial chest radiographs (CT scans) and serial pulmonary function tests (spirometry, diffusion capacity, 6 minute walk distance). These procedures and routine laboratory tests will not be repeated specifically for this study if they are deemed to be clinically indicated. The results of these standard of care procedures will be extracted from the participant's medical record and used as research data. All enrolled subjects will also have serial measures of circulating autoantibodies.

Patients will be monitored carefully for occurrences of adverse events. Adverse experiences will be evaluated according to criteria outlined in the NCI Common Terminology Criteria for Adverse Events (CTCAE), version 4.0.

Patients will be followed for nine (9) months after random assignment. Patients removed from treatment due to unacceptable adverse events will be followed throughout the 9 months under the principle of intent to treat.

2.3 INCLUSION AND EXCLUSION CRITERIA

Potential subjects will be identified by attending physicians (i.e., collaborating center Co-Investigators or their designees). Subjects who sign informed consent will be assigned a deidentified study ID and will be screened for inclusion and exclusion criteria.

Inclusion Criteria

- 1) Diagnosis of IPF, not established >5 years from the date of enrollment, that fulfills ATS/ERS Consensus Criteria (1).
- 2) Ability and willingness to give informed consent.
- 3) Age 50-85 years old.
- 4) Ambulatory.
- 5) Presence of autoantibodies against HEp-2 cells.*

*HEp-2 autoantibody determinations will be performed in peripheral blood specimens from potential subjects who otherwise fulfill all inclusion and exclusion criteria, AFTER they have given written informed consent. Specimens from potential subjects will be shipped to the central laboratory of the PI ([name]) at the University of Alabama at Birmingham for these assays.

Exclusion Criteria

- 1) Diagnosis of current infection, proven or suspected by participating physicians based upon their clinical assessments.
- 2) Presence of active hepatitis B or C, or HIV infection.
- 3) History or presence of conventional autoimmune syndromes (e.g., systemic lupus erythematosus, scleroderma, rheumatoid arthritis, myositis, anti-neutrophil cytoplasmic antibody vasculitis, Sjogren's syndrome, Goodpasture's syndrome) by clinical evaluation or positive conventional autoimmune serologic tests, i.e., ANA, RF, ANCA, Anti-Ro, Anti-LA, Anti-RNP, ANCA, Jo-1).
- 4) History of reaction to murine-derived products or any of the trial medications, or prior exposures to human-murine chimeric antibodies.
- 5) Malignancy, excluding basal or squamous cell skin cancer and low-risk prostate cancer, defined as stage T1 or T2a with PSA less than 10 ng/dl. Rituximab is not known to promote cancer progression, and these criteria are within current guidelines.
- 6) Unwillingness to complete post-treatment surveillance for 9 months.
- 7) Diagnosis of major morbidities (aside from IPF) expected to interfere with subjects' study participation for 9 months.
- 8) Treatment for >5 days within the preceding month with >10 mg. prednisone (or equivalent corticosteroid) or any treatment during the preceding month with a potent cellular immunosuppressant (e.g., cyclophosphamide, methotrexate, mycophenolate, azathioprine, calcineurin inhibitors, etc).
- 9) Uncontrolled diabetes or hypertension that precludes safe treatment with methylprednisolone.

- 10) Concurrent participation in other experimental trials.
- 11) Pregnancy or unwillingness to use contraception during the duration of the study among female participants with child-bearing potential. The safety of rituximab during pregnancy has not been established.
- 12.) Ratio of forced expiratory volume in 1 second to forced vital capacity (FEV $_1$ /FVC) <70% of predicted values.

Subjects who fulfill all inclusion criteria and meet no exclusion criteria will be eligible for randomization.

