2.6.1 Screening and Randomization (see Table 1 and Appendix A)

Patients will undergo the screening assessment to determine that all inclusion/exclusion criteria are met prior to receiving the study drug treatments. The following tests and procedures will be performed prior to randomization to verify eligibility:

Eligibility Screening (Days -14-to-0):

The screening assessment may take place over more than one day to rule out infections and to confirm the diagnosis of IPF.

- Informed Consent
- Medical History
- Physical exam.
- Laboratory evaluations to exclude the presence of conventional autoimmune syndromes (ANA, RF, ANCA, Anti-Ro, Anti-LA, Anti-RNP, Jo-1, and C3/C4) and CBC with differentials and platelet counts. These tests are standard of care evaluations for IPF patients.
- Tests for hepatitis B surface antigen (HBsAg) and anti-hepatitis B core (HBc) antibodies, and Hepatitis C and HIV antibodies.
- Anti-HEp-2 autoantibody titer determinations.
- Serum pregnancy test for women of childbearing potential.
- Baseline symptom assessment

Summary of Eligibility Determinations/Screening Procedures:

	SEQUENCE OF EVENTS			
	1	2	3	4
Medical Record Review to Begin Eligibility Ascertainment	x			
Sign Informed Consent		х		
Protocol Specific Tests: Anti-HEp-2 Auto- antibody, Hepatitis, HIV, Pregnancy Conventional autoantibodies (ANA, RF, etc.)			x	
Randomization				х

Table 1. Processes and sequences of eligibility determinations. Sequences denote the order of these processes. Randomization should occur within 14 days of obtaining informed consent (thereby allowing time for anti-HEp-2 specimen shipping to the central laboratory, and performing these assays).

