2.6.2 Experimental procedures (see also Table 2 and Appendix A)

Pretreatment:

Patients that meet all inclusion/exclusion criteria will be randomized to receive one of the study treatments as described above. Baseline studies to be performed within 14 days prior to the first study treatment include:

- Laboratory evaluations: complete blood count (CBC) with differential and platelet count, performed at the respective collaborating centers. These are standard of care tests.
- Blood draw and specimen shipment to the Coordinating Center lab for HEp-2 autoantibody, anti-HSP70 autoantibody, initial C3, C4, viral studies, lymphocyte phenotypes, and B-cell mediator studies- see also Section 2.6.1 and Table 1) A total of 29 ml of blood will be procured at this time for various assays and experimental studies..
- Pulmonary function tests (complete spirometry, DLCO, 6 minute walk distance, O₂ requirement and saturations at rest and with exertion, Borg scale dyspnea assessment).
- Chest CT scan within 30 days prior to randomization and first study treatment.

Day 1 (first treatment):

- Review of study protocol with subject, confirmation of subject's understanding of protocol and informed consent.
- Physical exam and assessment to include vital signs and blood pressure.
- First administration of study medications.

Day 2 (one day after first treatment):

Phone interview to assess for new symptoms and AE.

Day 14 (after first treatment):

- Physical exam and assessment to include vital signs and blood pressure.
- Second administration of study medications.

Day 15 (one day after second treatment):

Phone interview to assess for new symptoms and AE.

Month 1 (after first treatment):

- Physical exam and assessment to include vital signs and blood pressure.
- Current medication assessment
- Laboratory evaluations: complete blood count (CBC) at the respective collaborating centers
- Blood draw and specimen shipment to the Coordinating Center lab for experimental autoantibodies, serial C3, C4, lymphocyte phenotypes, and B-cell mediator studies. A total of 29 ml of blood will be procured at this time for CBC and experimental immunology tests
- Pulmonary function tests (complete spirometry, DLCO, 6 minute walk distance, O₂ requirement and saturations at rest and with exertion, Borg scale dyspnea assessment).
- AE assessment

Month 2 (after first treatment):

• Phone interview to assess for new symptoms and AE.

Month 3 (after first treatment):

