The mechanisms responsible for beneficial clinical effects of rituximab are complex and incompletely understood, but include elimination of autoantigen-reactive CD20⁺ memory cells (plasma cell precursors), as well as alterations of B-cell antigen presentation, or B-cell costimulatory and/or chemotactic functions. Rituximab obviates or reduces deleterious effects of pathogenic autoantibodies. It has been used in thousands of patients over many years, and has a well-characterized and acceptable safety profile, unlike other much more experimental anti-B-cell agents (e.g., alemtuzumab, bortezomib, etc.). These other treatments are less specific, more toxic, and have only rarely been used in autoimmune patients. Their safety and efficacy for therapy of autoantibody diseases are unknown.

Reported serious adverse events (AE) following rituximab treatment include fatal transfusion reactions, although these seem to occur primarily in lymphoma patients and may be indistinguishable or overlap with tumor lysis syndrome (29-39,42) Serious transfusion reactions to rituximab have occurred in <1% of RA patients. Reactions occurring in >5% of these subjects were nausea (8%), hypertension (8%), upper respiratory tract infections (7%), and arthralgia (6%). Corresponding event rates in placebo controls were: 5%,5%,6%, and 4%, respectively. Uncommon or rare events include mucocutaneous reactions, progressive multifocal leukoencephalopathy, hepatitis B reactivations, and rare infections (29-39,42).

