5.1.2 Potential Risks of Experimental Interventions

The risks of steroid (methylprednisolone) (used as a premedication):

Common: insomnia, nausea, vomiting, or stomach upset; fatigue or dizziness; muscle weakness or joint pain; problems with diabetes control; or increased hunger or thirst.

Rare: acne, increased hair growth, thinning of the skin, cataracts, glaucoma, osteoporosis, roundness of the face, and changes in behavior

The risks of acetaminophen (Tylenol) (used as a premedication):

Uncommon risks include liver or kidney toxicities. In the doses used here these risks are rare.

The risks of diphenhydramine (Benadryl) (used as a premedication):

Common risks are drowsiness. Other, less common risks include dry mouth, urinary retention, cardiac rhythm disturbances, confusion.

The risks of Rituximab:

Common Risks: Fever, chills, headache, pain, rash, pruritus, angioedema, nausea, abdominal pain, cytopenias, weakness, cough, rhinitis. Infusion related reactions: angioedema, bronchospasm, chills, dizziness, fever, headache, hyper-/hypotension, myalgia, nausea, pruritus, rash, rigors, urticaria, and vomiting.

Infrequent Risks: Hypotension, peripheral edema, hypertension, flushing, edema, dizziness, anxiety, agitation, depression, hypoesthesia, insomnia, malaise, nervousness, neuritis, somnolence, vertigo, migraine, urticaria, hyperglycemia, hypoglycemia, hypercholesterolemia, diarrhea, vomiting, dyspepsia, anorexia, weight loss, anemia, pain at the injection site, back pain, myalgia, arthralgia, paresthesia, arthritis, hyperkinesia, hypertonia, neuropathy, conjunctivitis, lacrimation disorder, throat irritation, bronchospasm, dyspnea, upper respiratory tract infection, sinusitis, LDH increased.

Other Risks: Rare events associated with rituximab include severe mucocutaneous reactions, progressive multifocal leukoencephalopathy due to LC virus reactivation, hepatitis B reactivations, and other infections.

The risks of placebo:

Placebo contains no active medication. It is unlikely to be associated with any side effects.

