APPENDIX A. STUDY ASSESSMENT TABLE AND EVENTS

Visit Number	Pre-Treatment		Treatment				Post Treatment Follow-Up								
	1	2	3	4	5 ^β	6	7#	8	9 [‡]	10	11	12 [‡]	13	14	15 [‡]
Day (D) or Month (M) from First Treatment	Screen*	Base Line*	D 1	D2	D 14	D 15	M 1	M 2	M 3	M 4	M 5	M 6	M 7	M 8	M 9
Informed Consent	x														
Inclusion Exclusion Criteria	×														
History and Medication Review	x		x		×		х		x			x			×
Physical Exam	x		х		х		х		х			х			x
Screening Lab Tests: ANA,RF, anti-Ro, Anti-La, anti-RNP, anti-Jo-1, HCV, HBsAg, HBcAb, HIV Ab, serum pregnancy test	x														
Complement (C3,C4)		×					×		х.			×			x
CBC/Diff/plat		x			_		x		х			×			×
Chest CT scan		×													×
Spirometry, DLCO, Exercise SaO2, 6 min walk, Borg		x					x		x			x			x
Experimental Immunology		x					x		x			х			х
Randomization (1:1)			х												
Study Treatment			х		x										
AE Assessment	х	х	x	х	x	х	х	х	x	х	х	х	х	x	х
Phone assessment				×		х		х		х	x		х	x	
Study Completion															x

^{*}Screening and Baseline evaluations can occur concurrently, or on separate days, as long as all tests and procedures are performed in the 14 days prior to first study treatment. Chest CT can be performed within the 30 day interval prior to first study

[#] The Months 3, 6 and 9 have a +/- seven day window.

The Month 1 visit has a +/- five day window.

The Months 3, 6 and 9 have a +/- seven day window.

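### Exclusion 2 bars only *active* hepatitis B and leaves the word undefined, so a site may randomize an HBsAg-negative, anti-HBc-positive subject and still comply, with no hepatitis B or liver test scheduled after screening

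*Combined protocol and SAP*

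**What the plan says.** **Eligibility.** Exclusion 2 in Section 2.3 is "Presence of active hepatitis B or C, or HIV infection". The synopsis has the same wording, and neither place defines *active*. Section 2.3 closes with the default: "Subjects who fulfill all inclusion criteria and meet no exclusion criteria will be eligible for randomization". Exclusion 1 leaves room for judgement: "Diagnosis of current infection, proven or suspected by participating physicians based upon their clinical assessments".

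**Screening tests.** Section 2.6.1 lists, among the tests done before randomization to verify eligibility, "Tests for hepatitis B surface antigen (HBsAg) and anti-hepatitis B core (HBc) antibodies, and Hepatitis C and HIV antibodies". Appendix A repeats them ("HCV, HBsAg, HBcAb, HIV Ab, serum pregnancy test") and marks them in the screening column only.

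**Risk.** Section 3.4 states: "Uncommon or rare events include mucocutaneous reactions, progressive multifocal leukoencephalopathy, hepatitis B reactivations, and rare infections". The rare risks of rituximab in Section 5.1.2 include "progressive multifocal leukoencephalopathy due to LC virus reactivation, hepatitis B reactivations, and other infections".

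**After screening.** The pretreatment blood draw in Section 2.6.2 lists "initial C3, C4, viral studies, lymphocyte phenotypes, and B-cell mediator studies" and points back to Section 2.6.1. The draws at months 1, 3, 6 and 9 list blood counts, complement, autoantibodies, lymphocyte phenotypes and B-cell mediators. Viral studies are not among them.

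**The concern.** Reactivation, by its meaning, concerns an infection that is not active at the time. A subject who is HBsAg-negative and anti-HBc-positive is the one for whom the named risk is relevant, and also the one whom the word *active* need not exclude. The test that would identify this subject is already ordered for eligibility, but its result leads to no stated action: no exclusion, further test, prophylaxis or added monitoring.

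Exclusion 3 shows the missing link. There, positive results on named autoimmune serologic tests exclude. Exclusion 2 has no such tie between result and decision.

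Two things are at stake. The first is patient safety: such a subject in Arm A would receive two 1 g infusions with no scheduled test that would show reactivation. The second is consistency: five sites with no rule could handle the same laboratory result differently.

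**Working it through.** The plan gives no figure on this point, so the check is mainly a reading of the text followed by a count.

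**1. Following one subject through the criteria.** Take a candidate who is HBsAg-negative and anti-HBc-positive, has no signs of infection, and is otherwise eligible.
- Exclusion 2: not met if *active* is read as current infection. Nothing in the documents requires another reading.
- Exclusion 1: met only if a physician chooses to treat the result as a current infection, proven or suspected. Anti-HBc is not mentioned there.
- No other exclusion names hepatitis B.
- By the closing rule of Section 2.3, the candidate is eligible.

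A site that randomizes this subject has not departed from the protocol. A site that declines could defend that too.

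**2. Counting scheduled tests.** Appendix A shows these contacts after the first infusion: day 2, day 14, day 15 and months 1 to 9, so 3 + 9 = 12. I compared them with the visit lists in Section 2.6.2 and with Table 2.

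| Item | Scheduled |
|---|---|
| Adverse event assessment | 12 of 12 contacts |
| Hepatitis B serology, hepatitis B DNA or liver test | 0 of 12 contacts |
| The same, at the laboratory visits (months 1, 3, 6, 9) | 0 of 4 |
| The same, at day 14 before the second infusion | 0 |

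No baseline liver test is scheduled either.

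**3. Cost of excluding on anti-HBc.** Let p be the share of otherwise eligible candidates who are HBsAg-negative and anti-HBc-positive. The documents do not give p, so 1%, 5% and 10% are assumed. To randomize 58, the extra number screened is 58/(1 − p) − 58:
- p = 0.01: 58/0.99 − 58 = 0.6
- p = 0.05: 58/0.95 − 58 = 3.1
- p = 0.10: 58/0.90 − 58 = 6.4

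**4. Exposure, as illustration only.** With the same p, and if every such candidate were admitted, the expected number in Arm A is 29p, and the chance of at least one is 1 − (1 − p)^29:
- p = 0.01: 0.3 subjects; 25%
- p = 0.05: 1.5 subjects; 77%
- p = 0.10: 2.9 subjects; 95%

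The width of this range comes from the assumption and not from trial data.

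**5. Effect on the design.** The planned 29 per arm rests on 33% versus 3% at two-sided 0.05. Exact enumeration of the two-sided Fisher test gives 81.0% power, in line with the stated 80%. None of these inputs depends on the wording of exclusion 2.

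**The case against.** **Sites may already exclude these subjects.** *Active* is undefined, anti-HBc is ordered to verify eligibility, and exclusion 1 covers suspected infection. Section 3.2 says the exclusions are meant to keep out patients at increased risk from rituximab. Section 3.3 prefers to exclude equivocal infections, although its subject there is occult lung infection. This stands in part. A reader might infer that the protocol has decided to admit anti-HBc-positive subjects; the documents do not support that. What they show is an unstated rule that sites may apply either way.

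**Liver problems could still be detected.** A reader might infer that no subject will have a liver test after screening. That goes too far. Section 2.6 leaves other routine care to the primary physician, Section 2.2 takes standard-of-care results from the medical record, and a laboratory abnormality is among the individual stopping grounds in Section 5.4.3.3. The count of 0 of 12 describes the protocol's schedule only. Whether routine care includes liver tests is not stated.

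**Section 5.5.2 names no hepatitis B protection.** Little follows from this. That list is not presented as exhaustive, and the screening serology is itself a safeguard.

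**The event is rare.** The protocol says so and gives no reactivation rate. The 25% to 95% above is the chance of enrolling at least one such subject in Arm A under assumed prevalences. It must not be read as a chance of harm.

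**Hepatitis C looks similar.** The only hepatitis C test ordered is an antibody, and the handling of a positive result is unstated. A reader might infer that the antibody should exclude as well. The documents name no hepatitis C risk from rituximab, so they give no safety argument for that.

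**Conclusion.** The point holds as a gap in the eligibility rule. As written, a site may give rituximab to an HBsAg-negative, anti-HBc-positive subject and remain compliant, and the protocol schedules no test afterwards that would show the reactivation it names as a risk. This rests on the text alone and needs no assumed figure.

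The size cannot be estimated. The documents give neither an anti-HBc prevalence nor a reactivation rate, and they describe the event as uncommon or rare. The case for acting is that the hazard is foreseeable, the protocol names it, and it can be avoided with a result already in hand. I would class the change as one that should be made: a cheap improvement in patient safety, with no bearing on the validity of the primary comparison.

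**What to change.** In the synopsis and in Section 2.3, replace the hepatitis B part of exclusion 2 with: *Positive HBsAg or positive anti-HBc*. Leave the hepatitis C and HIV wording as it is.

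Other handling is possible, such as hepatitis B DNA testing with prophylaxis and serial monitoring. That is a clinical choice for the sponsor, and it would add tests. Exclusion uses only results already drawn, and it fits the stated aim in Section 3.2 and the surplus of candidates claimed in Section 3.3.

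Cost: no new test, and no change to the sample size of 58 or to the primary analysis. There would be some additional screen failures, number unknown; the working gives about 0.6 to 6.4 more candidates screened for the assumed 1% to 10%. The change also needs a routine amendment at five centers, each of which has 90 days to supply its IRB approval (Sections 6.3.2 and 6.5).
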